15.1. Data Collection during COVID-19 Pandemic

On March 18, 2020 the American Academy of Ophthalmology (AAO) issued a statement which included guidelines based on the recommendations from the American College of Surgeons and the CDC.

Investigational clinical sites will follow the academy guidelines for providing elective ophthalmic care. As part of these guidelines the AAO recommended protocols for scheduling and seeing patients as well as environmental cleaning and disinfection. Following these guidelines should greatly mitigate the risks for subjects who have to return to the clinic for follow-up or routine visits. Mitigating these risks will allow for reliable collection of high-quality data being collected from each clinical site following the subject visit.

15.2. Device Accountability

The Investigator will be responsible for keeping current and accurate records of the amount of Intraoperative Implantable Pseudophakic Contact Lenses (IOPCLs) received, implanted, and disposed/returned. The IOPCLs must be stored in a secure area and are to be implanted only in subjects enrolled in the study, in accordance with the conditions specified in this protocol. Accountability records will include.

- o The lot numbers/serial numbers of the lenses received, the receipt date, and the quantity received.
- o The names of the people who received, used, or disposed of the lenses.
- o A record of each subject implanted with the lenses.
- o Quantity of IOPCL's returned at the completion of enrollment.

15.3. Protocol Deviations

Protocol deviations will be grouped based on severity. Major/Important deviations are a subset of protocol deviations that might significantly affect the completeness, accuracy, and/or reliability of the study data or that might significantly affect a subject's rights, safety, or well-being. For example, important protocol deviations might include enrolling subjects in violation of key eligibility criteria designed to ensure a specific subject population or failing to collect data necessary to interpret primary endpoints, as this may compromise the scientific value of the trial. Protocol deviations will be grouped by type will be recorded.

15.4. Study Completion Procedures

15.4.1 Subject Completion

Subjects are considered to have completed the study if they have completed all follow-up examinations through 330-420 days (12 months) including post-removal examinations.

15.4.2 Subject Termination

Subjects may be terminated from the study at the discretion of the Investigator only for reasons related to the study treatment regimen that would jeopardize their health and/or welfare if they were to continue in the study. Terminated subjects will not be replaced. However, every effort will be made to follow terminated subjects for safety reasons using the appropriate case report forms until the planned end of the study period.

15.4.3 Subject Discontinuation

Subjects may be discontinued from the study for non-treatment-related reasons only when no other option is possible. Reasons for

discontinuation include, but are not necessarily limited to, 1) voluntary withdrawal from the study by the Subject; 2) subject has moved from the area and is determined to be lost to follow-up; 3) Subject is unwilling or unable to cooperate with study requirements (non-compliance with post-operative follow-up visits, etc.).

Prior to discontinuing a Subject, every effort should be made to contact the Subject in an effort either to get the Subject back into compliance with the protocol or to obtain as much follow-up data as possible regarding the Subject's current visual status.

16. Data Reporting

A Case Report Form binder will be provided by the Sponsor for each subject who is enrolled in the study. The appropriate case report form will be completed and signed by the Investigator/examiner at each examination. All case report forms will be completed in a legible manner in ink. Any corrections will be made by drawing a single line through the incorrect entry and initialing and dating the change. Information transferred from the source document will be faxed to the sponsor.

All forms will be reviewed for completeness and evident recording errors will be rectified by contact with the appropriate persons at the clinical site. Corrective and preventative actions will be implemented to avoid repeat errors. Double entry routines will be used to minimize data entry errors, and computerized editing routines will be used to identify unusual data entries for verification prior to statistical analysis. Data analysis will be performed per the statistical analysis plan in Appendix 6.

17. Recording of Data and Retention of Documents

Subject data will be documented in an anonymous fashion and the subject will be identified by the subject enrollment number. If, as an exception, it is necessary for safety or regulatory reasons to identify the subject, the Sponsor or its representative and the Investigator are bound to keep this information confidential.

The Investigator must retain essential documents indefinitely after the completion of the study, unless otherwise notified by the Sponsor. The Investigator agrees to adhere to the document retention procedures when signing the protocol Investigator statement of approval.

Essential documents include but are not limited to the following:

- IRB approvals for the study protocol, all amendments and informed consent form(s)
- IRB annual study review,

04-08-2021 20

- Subject's signed informed consent form,
- Correspondence from and to the Sponsor, and
- Any other documents relevant to the conduct of the study.

18. Study Monitoring

OnPoint Vision Inc. personnel (or designees) will monitor all clinical studies in a manner consistent with good clinical practices (GCPs) and all applicable health authority regulations, and in accordance the study monitoring plan. Study monitoring will involve the following elements.

- 1. OnPoint Vision Inc. personnel (or designee) will meet with the investigator(s) prior to the initiation of the study in order to review the adequacy of the subject population, facilities, and equipment with respect to the needs of the study, and to familiarize the investigator with the study protocol.
- 2. OnPoint Vision Inc. personnel (or designee) will meet with the investigator(s) at the time study subjects begin to be enrolled in order to ensure that subjects are being properly selected and that study data are being correctly recorded.
- 3. OnPoint Vision Inc. personnel (or designee) may remotely review and audit or visit the clinical site at any time during the study to review the case report forms and verify data against medical records.
- 4. Interim monitoring visits and telephone consultation will occur as necessary during the course of the study to ensure the proper progress and documentation of the study findings.

Sponsor field staff under the supervision of the investigator will periodically visit investigational sites to ensure that study procedures (e.g., refractions, visual acuity measurements) are performed consistently and in compliance with protocol-specified techniques, and in doing so may come in direct contact with study subjects. The rights and well-being of subjects are protected, and the study is being conducted in accordance with 21CFR, Parts 50, 54, 56 and 812.42 (U.S.C 282(j)). ISO 14155 (2011) Clinical investigation of Medical Devices for Human Subjects, ISO 11979-7, and applicable local regulations and the ethical principles laid down in the Declaration of Helsinki (see Appendix 4).

During the course of the study, if an Investigator is determined to be non-compliant with the study plan and/or applicable regulatory requirements, the Sponsor will take action to secure compliance. In addition, the Sponsor may terminate the Investigator's participation in the study if appropriate or the Investigator remains non-compliant despite the Sponsor's actions.

18.1 Remote Study Monitoring – COVID-19

This Remote Monitoring Plan has been developed by On-Point Vision to document the remote monitoring procedures for the CIIPCL-018 protocol that have arisen due

to the COVID-19 pandemic. Per FDA Guidance on Conduct of Clinical Trials of Medical Products during COVID-19 Public Health Emergency (May 14, 2020), On-Point Vision will be implementing remote monitoring as the COVID-19 pandemic has delayed on-site monitoring of the On-Point Vision protocol under IDE G190323. On-Point personnel are in active direct contact with sites via email and telephone to review study procedures, trial participant status, and study progress.

Remote monitoring procedures are being implemented on a larger scale as clinical research sites or study personnel are not comfortable with allowing on-site monitoring visits due to the increased risk of infection. Additionally, travel restrictions have further restricted access to clinical sites and the ability to perform on-site monitoring visits. These expanded remote monitoring guidelines may be continued through study completion, even after the COVID-19 issues are resolved.

The goal of remote monitoring is consistent with all monitoring, in that it is to assure that the rights and safety of all subjects are protected and ensure the quality and integrity of the data.

The On-Point monitor will provide the clinical site with a list of documents requested based on queries or data pending review. These documents will be uploaded to a secure site which is HIPPA compliant. The site will upload the necessary source documents to the monitor for review. Any documents uploaded to the monitor must have all subject identifiers (e.g. subject name, initials, date of birth) redacted. No additional personnel or email addresses should be copied on this correspondence from the site.

The monitor may request documents from the Regulatory binder for review, but a full regulatory document review will be done at an on-site visit after restrictions have been lifted and monitors are allowed back into the practices.

On-Point will carefully document situations where monitors were unable to access, or had to delay monitoring of a clinical site. On-Point personnel and monitors will document protocol deviations, or other GCP non-compliance issues identified at the clinical sites whether delayed identification was due to postponed monitoring.

Remote monitoring activities, including remote review of source documents, will be documented in the same level of detail as on-site monitoring activities, and any resulting actions to address issues identified from the remote source document review should be consistent with procedures and processes described in the study monitoring plan.

19. Confidentiality

All study data generated as a result of this study will be regarded as confidential, until appropriate analysis and review by the Sponsor or its designee and the Investigator(s) are completed. The results of the study may be published or presented by the Investigator(s) after the review by, and in consultation and agreement with, the Sponsor, and such that

04-08-2021 22

confidential or proprietary information is not disclosed. Prior to publication or presentation, a copy of the final text should be forwarded by the Investigator(s) to the

Sponsor, or its designee, for comment. Such comments shall aim to ensure the scientific integrity of the proposed publications and/or presentations and ensure that the data and material referring to OnPoint Vision Inc. products and activities receive fair, accurate, and reasonable presentation.

20. Appendices

Appendix 1 – Informed Consent Document

Appendix 2A – Schedule of Visits and Procedures

Appendix 2B – Schedule of Visits and Procedures after AccuraSee Removal

Appendix 3 – Clinical Methods

Appendix 4 – Declaration of Helsinki

Appendix 5 – Investigators Responsibility with Clinical Trial Agreement

Appendix 6 – Statistical Analysis Plan

Appendix 7 – Quality of Vision (QoV) Questionnaire

Appendix 8 – Case Report Forms

04-08-2021 23

1 INTRODUCTION

This Statistical Analysis Plan (SAP) outlines the statistical methods to be implemented within the scope of Protocol CIIPCL-18, entitled "Early Feasibility Study to Evaluate the Safety and Effectiveness of the AccuraSeeTM for Secondary Implantation in the Capsular Bag to Correct Residual Refractive Errors of Previous Cataract Surgery." Results of the proposed analyses will become the basis of the clinical study report for this protocol.

The purpose of this plan is to provide specific guidelines from which the analysis will proceed. All planned analyses specified in this document will be performed. Any changes to this plan, in the form of "post hoc" or "data driven" analyses will be identified as such in the final clinical study report. Any changes will either be reflected in amendments to this plan before the database lock or specifically documented in the clinical study report.

2 STUDY OBJECTIVE

The objective of this study is to determine if the intraocular pseudophakic contact lens (IOPCL), referred to as the AccuraSee, corrects residual refractive errors using a plus powered lens in subjects with ocular pathology previously implanted with an AcrySof® IQ monofocal intraocular lens and to confirm its positional stability and adherence relative to the intraocular lens.

The primary objective of this study is to determine the stability of the AccuraSee to successfully adhere to a pseudophakic intraocular lens without rotation or slippage.

The secondary objective of this study is to determine if the AccuraSee can successfully correct refractive errors up to +/- 3.0 diopters (D) in subjects previously implanted with an AcrySof® IQ monofocal intraocular lens.

3 STUDY ENDPOINTS

3.1 Effectiveness Endpoint

3.1.1 Primary Effectiveness Endpoint

The primary effectiveness endpoint identified for this Early Feasibility Study for AccuraSee.

• Proportion of eyes (≥ 50%) able to achieve a stable target refraction within 0.5 D of the intended target. Stability is achieved when there is no change (±0.50 D) in MRSE within two consecutive postoperative visits at 1 month or later visits.

3.1.2 Additional Effectiveness Outcomes

Other important effectiveness outcomes include the following visual acuity measurement:

Monocular uncorrected distance visual acuity (UCDVA)

These effectiveness outcomes will be summarized descriptively for different lens groups. The differences between preoperative and postoperative results will also be summarized by descriptive statistics. The 95% confidence intervals of mean difference may be provided.

3.2 Safety Endpoints

Preservation of Best Corrected Distance Visual Acuity (BCDVA)

The preservation of BCDVA is defined as proportion of eyes (< 5%) that lose two or more lines of BCDVA from baseline.

• Successful Delivery of the IOPCL as determined at 7-14 days post-operative

The successful delivery of the IOPCL is defined as no capsular tear, visualize centration between the IOL and IOPCL, no visible damage to either the IOL or IOPCL, and uniform leaflet coverage of all IOPCL haptic tabs.

• Long-term Adherence and Positional Stability

The long-term adherence and positional stability is defined as minimal change (i.e. \pm 10 microns) between 1-2 months and 4-6- months as determined by UBM measurements. The open central spacing between the IOL and IOPCL is established and maintained using UBM imaging.

Adverse Events

The Adverse Events is defined as characterization and incidence of cumulative and persistent intraoperative and post-operative adverse events.

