To determine if the intraocular pseudophakic contact lens (IOPCL), referred to as the AccuraSee, provides refractive correction using a plus powered lens in subjects with ocular pathology previously implanted with a Bausch and Lomb LI61AO or LI61SE monofocal posterior chamber intraocular lens (PCIOL) and to confirm its positional stability and adherence relative to the PCIOL.

Study Design:

This will be a 12-month three center study, in which a maximum of 10 pseudophakic subjects will be enrolled.

This study is being conducted in accordance with 21 CFR Parts 50, 54, 56 and 812.42 (U.S.C 282(j)). ISO 14155 Clinical investigation of Medical Devices for Human Subjects, ISO 11979-7, and the ethical principles laid down in the Declaration of Helsinki.

1. Introduction and Rationale

The AccuraSee (intraocular pseudophakic contact lens) consists of a 4.5 mm diameter concave-convex optic with three opposing haptic straps, or tabs. The haptic straps are designed to enter and rest within three channels created under the anterior leaflet of the capsular bag. Each channel is created with a Cady-Soiseth Capsule Separator spatula. Each haptic strap or tab has a small pawl, or ridge on the bottom that is used to catch and lock on to the IOL optic edge. This pawl aids in both centering the AccuraSee on the IOL optic as well as allowing the haptic strap to stay securely seated while contained under the surface tension of the anterior leaflet of the capsular bag. The lens is designed to fine-tune the residual refractive error of the longstanding pseudophakic eye. The lens design, position and surgical approach are intended to lessen the complication rate and overall invasive nature of today's available secondary lens implantation technologies.

2. Study Objective

The primary objective of this study is to determine the stability of the AccuraSee to successfully adhere to a pseudophakic intraocular lens without rotation or slippage.

The secondary objective of this study is to determine if the AccuraSee can successfully change refraction up to +3.0 diopters (D) in subjects previously implanted with an Bausch and Lomb LI61AO and LI61SE monofocal intraocular lens.

Safety Endpoints

- Preservation of BCDVA Proportion of eyes (< 5%) that lose two or more lines of BCDVA from baseline.
- Successful delivery of the IOPCL as determined at 7-14 days post-operative
 - o No capsular tear
 - o Visualize centration between the PCIOL and IOPCL

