 - o No visible damage to either the PCIOL or the IOPCL
 - o Uniform leaflet coverage of all IOPCL haptic tabs
- Long-term adherence and positional stability
 - Minimal Change in uniformity of the gap between 1-2 months and 4-6-months as determined by UBM measurements. Minimal change is defined as +/- 10 microns between visits is established and maintained using UBM imaging
- Characterization and incidence of cumulative and persistent intraoperative and post-operative adverse events.

Stopping Rules

The Sponsor or the clinical investigator can suggest suspension of the clinical trial at any time if they are in receipt of information that leads them to believe that continuing the study jeopardizes the health and welfare of the clinical trial participants. Suspension of the study will be considered if two or more consecutive severe ocular injuries occur at any one clinical site that are related to the surgical procedure and/or IOPCL device. A severe ocular injury results in a permanent impairment of a vision or permanent damage to an eye.

Examples:

- Uveitis-Glaucoma-Hyphema (UGH) Syndrome. Intraocular chafing from the IOL/PCIOL implant leading to a spectrum of iris transillumination defects and pigmentary dispersion to microhyphemas with elevated intraocular pressure.
- Posterior capsule rupture with IOL/PCIOL dislocation resulting in a posterior vitrectomy during the surgical procedure

Primary Effectiveness Endpoint

Proportion of eyes ($\geq 50\%$) able to achieve a stable target refraction, (manifest or autorefraction) within 0.5 D of the intended target. Stability is achieved when there is no change (± 0.50 D) within two consecutive postoperative visits at 1 month or later visits.

04-08-2021 5

3. Subject Population

A maximum of 10 pseudophakic eyes will be implanted unilaterally with the AccuraSee IOPCL.

3.1. Inclusion Criteria:

- 1. Subjects who have already had cataract surgery with a Bausch and Lomb monofocal intraocular lens model LI61A0 (with lens power from 18.0 diopters (D) to 23.0 D) or model LI61SE (with a lens power from18.0 D to 22.5 D), as clearly evidenced by photographic documentation with one of the following: (1) patient medical record, (2) clinic chart with labeling attached, (3) surgical record with labeling attached, or (4) patient identification card with make, model, power, and serial number.
- 2. Able to comprehend and sign a statement of informed consent.

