10.2 Unscheduled / Interim Visits

Additional visits may be scheduled as deemed necessary by the investigator, to ensure the safety and well-being of the subject.

11. Clinical Assessments

All parameters will be recorded for both eyes at baseline (pre-operative). Measurements will be recorded for the study eye at postoperative and post-removal visits. See Appendix 2A schedule of visits (pre and post-operative visits) and Appendix 2B (post-removal visits). See Appendix 3 for clinical assessment instructions

- Inclusion/exclusion criteria: Preoperative
- Medical history: Preoperative
- Demographics: Preoperative
- Patient Informed Consent: Preoperative
- Measurements: Make and Model # of Equipment Preoperative
- Axial Length & Keratometry Preoperative
- Capsulorhexis Size at the time of IOL surgery: Preoperative
- Position of IOL Haptics and IOPCL Incision Location: Preoperative
- Mesopic and Photopic Pupil size measured by Pupilometer: Preoperative

- Predicted Post-Op Refraction: Preoperative
- Pseudophakic IOL power with make and model number: Preoperative
- Spatial Visualization between the PCIOL and IOPCL Using UBM: 30-60 days, 120-180 days, 330-420 days, Interim.
- Recording of the IOPCL Surgical Procedure: Operative
- UCDVA: Uncorrected Distance Visual Acuity Preoperative, 7-14 days, 30-60 days, 120-180 days, 330-420 days. Interim
 - Post-removal, 7-14 days, 30-60 days, 120-180 days, 330-420 days. Interim
- UCIVA: Uncorrected Intermediate Visual Acuity Preoperative, 7-14 days, 30-60 days, 120-180 days, 330-420 days. Interim
 - Post-removal, 7-14 days, 30-60 days, 120-180 days, 330-420 days. Interim
- UCNVA: Uncorrected Near Visual Acuity Preoperative, , 7-14 days, 30-60 days, 120-180 days, 330-420 days, Interim.
 - Post-removal, 7-14 days, 30-60 days, 120-180 days, 330-420 days. Interim
- BCDVA: Best Corrected Distance Visual Acuity Preoperative, 7-14 days, 30-60 days, 120-18 days, 330-420 days, Interim
 - Post-removal, 7-14 days, 30-60 days, 120-180 days, 330-420 days, Interim
- Manifest Refraction: Preoperative, 7-14 days, 30-60 days, 120-180 days, 330-420 days, Interim
 - Post-removal, 7-14 days, 30-60 days, 120-180 days, 330-420 days, Interim
- Auto-refraction: Preoperative, 7-14 days, 30-60 days, 120-180 days, 330-420 days. Interim
 - Post-removal, 7-14 days, 30-60 days, 120-180 days, 330-420 days, Interim.
- Slit Lamp Examination: Preoperative, 1-2 days, 7-14 days, 30-60 days, 120-180 days, 330-420 days. Interim

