6 STATISTICAL CONSIDERATIONS

6.1 General Considerations

Descriptive statistics (mean, median, standard deviation, minimum, and maximum) will be used to summarize continuous variables. Frequencies and percentages will be used to summarize categorical variables.

Any analysis not described in this plan will be considered exploratory, and will be documented in the clinical study report (CSR) as a post hoc analysis or a change to the planned analysis.

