6.2 Sample Size

Sample size is limited to maximum of 10 subjects (eyes) for this Early Feasibility Study (EFS).

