7.5.1 Preservation of BCDVA

The analysis of this clinical outcome will be based on the observed data of AccuraSee IOPCL. The number and percent of IOPCL implanted eyes with a BCDVA loss of 2 or more lines from preoperative will be derived.

Additionally, if needed, data listing or summary will be provided for eyes with a BCDVA loss of ≥ 2 lines from the best BCDVA before the corresponding visits.

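### With at most 10 eyes, the under-5% limit on BCDVA loss can be met only by zero events, and zero events cannot support a 5% rate; no interval or judging visit is planned

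*SAP*

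**What the plan says.** SAP 3.2 (Safety Endpoints) gives the criterion: "The preservation of BCDVA is defined as proportion of eyes (< 5%) that lose two or more lines of BCDVA from baseline". The safety endpoints in Protocol section 2 carry the same limit: "Proportion of eyes (< 5%) that lose two or more lines of BCDVA from baseline". Neither names a visit.

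Protocol section 3 sets the size of the study: "A maximum of 10 pseudophakic eyes will be implanted unilaterally with the AccuraSee IOPCL". SAP 6.2 repeats the cap and describes the trial as an early feasibility study. Neither document derives the 10 eyes or the 5% limit from an error rate, an expected event rate or a target precision.

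For the analysis, SAP 7.5.1 says: "The number and percent of IOPCL implanted eyes with a BCDVA loss of 2 or more lines from preoperative will be derived". The general rule in SAP 6.1 is of the same kind: "Frequencies and percentages will be used to summarize categorical variables". The only confidence interval in the SAP is an optional one in section 3.1.2, for changes in the additional effectiveness outcomes: "The 95% confidence intervals of mean difference may be provided".

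Protocol section 11 schedules BCDVA as: "Best Corrected Distance Visual Acuity Preoperative, 7-14 days, 30-60 days, 120-18 days, 330-420 days, Interim". The third postoperative window is evidently 120-180 days, as for the other assessments. That makes four scheduled postoperative measurements plus any interim visits. SAP 6.8 places an interim analysis at 4-6 months and the final analysis after 12 months, but ties this criterion to neither.

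**The concern.** A limit written as a percentage below 5 suggests that some small number of losses is tolerable and that meeting the limit says something about a 5% rate. With 10 eyes or fewer neither is true. The rule allows no losses at all, and meeting it leaves much higher loss rates plausible. With only a number and a percent in the table, a result of 0% beside a limit of 5% would carry no sign of that uncertainty.

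The missing visit matters more than usual under a zero-event rule, because a single eye at a single visit settles whether the benchmark is met. Within SAP 3.2, successful delivery is fixed at 7-14 days and positional stability at 1-2 to 4-6 months. The BCDVA criterion has no such time point.

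**Working it through.** **Inputs from the documents.** Limit: under 5% (Protocol section 2; SAP 3.2). Maximum n: 10 eyes, one per subject (Protocol section 3; SAP 6.2). Missing data: available data only, no imputation (SAP 6.5), so the denominator at a visit can fall below 10.

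**Assumptions.** The documents give no confidence level, sidedness or expected loss rate. I use 95%, two-sided unless marked, and true loss rates from 1% to 30%. Eyes are treated as independent with a common loss rate. There is no sample-size or precision calculation in the plan to reproduce.

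**Step 1: attainable proportions.** The smallest non-zero proportion is 1/n. At n = 10 it is 10%; at n = 8 it is 12.5%. One event fits under 5% only when 1/n < 0.05, that is from n = 21 (1/20 = 5.0%, which is not below 5%; 1/21 = 4.8%). So for every n up to 10 the limit means zero events.

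**Step 2: what the best result can show.** For 0 of n, the exact (Clopper-Pearson) upper limit is 1 − a^(1/n), with a = 0.025 two-sided or 0.05 one-sided.

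| Result | Two-sided 95% upper limit | One-sided 95% upper limit |
|---|---|---|
| 0/10 | 1 − 0.025^(1/10) = 30.8% | 1 − 0.05^(1/10) = 25.9% |
| 0/8 | 1 − 0.025^(1/8) = 36.9% | 1 − 0.05^(1/8) = 31.2% |

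For comparison, 1/10 has a two-sided interval of 0.25% to 44.5%.

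**Step 3: eyes needed to exclude 5% with zero events.** Solve 0.95^n ≤ a, so n ≥ ln(a)/ln(0.95).

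- Two-sided 95%: ln(0.025)/ln(0.95) = 71.9, so 72 eyes.
- One-sided 95%: ln(0.05)/ln(0.95) = 58.4, so 59 eyes.

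The 72 is the figure that matches the two-sided interval proposed below.

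**Step 4: how often 0/10 would be seen.** The probability is (1 − p)^10.

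| Assumed true loss rate p | Probability of 0/10 | Probability of at least one loss |
|---|---|---|
| 1% | 90.4% | 9.6% |
| 2% | 81.7% | 18.3% |
| 5% | 59.9% | 40.1% |
| 10% | 34.9% | 65.1% |
| 20% | 10.7% | 89.3% |
| 30% | 2.8% | 97.2% |

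A loss rate of twice the limit would therefore still give 0/10 in about one study in three, and a rate well inside the limit would miss the benchmark in nearly one in five. These figures refer to a single determination per eye.

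**The case against.** The strongest reply is that this is an unrandomised, unmasked early feasibility study with descriptive summaries. No hypothesis, significance level or success decision is attached to the 5% figure, and suspension of the study depends on a separate rule about severe ocular injuries (Protocol section 2, Stopping Rules). The table will show the denominator, so a reader can see that 0% means 0 of about 10. All of that stands, and it limits the point to one of clarity and precision. It does not remove the point, because a numerical threshold is still written into a safety endpoint and the data cannot speak to it.

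A second reply is that the visit gap is partly covered: BCDVA is tabulated at every scheduled visit (SAP 7.5.5.1), and SAP 7.5.1 allows a listing of losses. This stands only in part. The listing is made only if needed and is measured from the best earlier acuity instead of baseline. The lowest category in the by-visit table is worse than 20/80, while Protocol section 3.1 admits eyes at 20/80 or worse; an eye that starts in that lowest category could lose two lines without changing category. Neither output assigns the criterion to a visit.

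A reader might infer more than the documents support:

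- **That the plan contains an arithmetic error.** No figure in it is miscalculated; the threshold and the sample size simply do not fit each other.
- **That one lost-line event would fail the device, or that 0/10 will be claimed as proof of a rate below 5%.** The plan says neither.
- **That the cap of 10 is wrong.** A feasibility cap needs no power calculation, and the 72 eyes only show the distance between the limit and the sample.
- **That judging at any of four visits raises the chance of a spurious loss by a stated amount.** The documents give no rate of chance two-line drops, and all visits in an eye share one preoperative value, so treating visits as independent would overstate the effect. I put no number on it.

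**Conclusion.** The point holds as a mismatch between threshold and sample size, together with an incompletely specified endpoint. That the limit means zero events follows from the cap of 10 alone and needs no assumption. That the best possible result cannot support 5% rests only on a conventional 95% level, and it is the same one-sided or two-sided. The probabilities by true loss rate rest on assumed rates and are illustrative. The absence of an interval and of a judging visit is read directly from SAP 3.2, 6.1 and 7.5.1. The plan should be amended on this point, but nothing here puts the conduct of the study in question.

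**What to change.** In Protocol section 2 and SAP 3.2, restate the criterion as a descriptive benchmark: 0 of n eyes with a loss of two or more lines from baseline, judged at one named visit. The 12-month visit is one candidate, with the 4-6 month result reported descriptively at the interim analysis. State n beside the result.

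In SAP 7.5.1, list every loss of two or more lines from baseline at any visit, scheduled or interim, and mark whether it persisted. Report the exact Clopper-Pearson 95% interval beside the percent. Add a sentence that the study does not establish a loss rate below 5%.

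Settle the wording before the results are examined. The cost is a wording change in two documents, one more table column and a less favourable safety statement; no further eyes are needed. The change does not remove the chance that a single loss misses a zero-event benchmark. It makes that feature visible, and the listing with persistence lets a reader judge such an event on its merits.
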